- ^h Heart rate, blood pressure, and respiratory rate are collected preinfusion, every 15 minutes (± 5 minutes) during the infusion, at the end of the infusion, and 1 and 2 hours (± 15 minutes) postinfusion. Body temperature will be collected preinfusion on dosing days.
- ⁱ Clinical safety labs include serum chemistry, hematology, urinalysis, and coagulation. Labs are collected preinfusion at dosing visits.
- ^j 12-lead ECGs are collected after 5 minutes of rest, in triplicate and at least 1-2 minutes apart. ECGs are collected within 2 hours prior to the start of the infusion. Unscheduled ECGs may be performed as clinically necessary.
- ^k Blood samples for PK and PD are collected within 2 hours prior to the start of the infusion at dosing visits. An additional sample is collected via peripheral IV 2 hours (± 1 hour) after completion of the infusion on Day 0, Day 140 (PK only), and Day 336 (PK only).
- ^l Blood sample for anti-SRK-015 antibody testing is collected within 2 hours prior to the start of the infusion at dosing visits.
- ^m Patients in Cohort 3 will be randomized to low- or high-dose SRK-015 within 24 hours prior to the first infusion on Day 0.
- ⁿ See [Table 6](#) for motor function outcome measures conducted for each cohort. Unscheduled motor function outcome measures may be performed as needed.
- ^o QOL collected using the PROMIS Fatigue Questionnaire and PEDI-CAT. If the PEDI-CAT and/or PROMIS are not available in the native language, they should not be completed. Unscheduled QOL questionnaires may be performed as needed.
- ^p Sites contact patients within 7 days following each infusion to collect information on adverse events and concomitant medications.

Table 3: Study Schedule of Assessments: Extension Period A (Extension A Visits 1-15)

Activity/Assessment	Extension Period A														Follow-Up/ Other		
	E1 364 ^c	E2 392	E3 420	E4 448	E5 476	E6 504	E7 532	E8 560	E9 588	E10 616	E11 644	E12 672	E13 700	E14 728	E - UNS	E15 812/EOS/ ET	
Informed Consent ^o	X																
Pregnancy Test ^d	For patients who enroll into Extension Period A, assessments will merge between Treatment Period Day 364 (V15) and Extension Period A Day 364 (E1). Study drug administration and PK/PD/ADA Sampling will only be performed for patients who enroll into Extension Period A.		X				X				X					X	
Weight ^e		X	X	X	X	X	X	X	X	X	X	X	X	X	X	X	X
Height ^f					X				X					X	X	X	
Physical Examination ^g		X		X		X		X		X		X		X	X	X	

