6.3.4. Individual Stopping Rules

Dosing for any individual patient may be suspended or discontinued if the patient experiences an SAE related to SRK-015 or a clinically significant non-serious AE related to SRK-015, that in the assessment of the Investigator and in consultation with the Medical Monitor, warrants suspension or discontinuation from further dosing for that patient's well-being. For patients who have had their dosing suspended, dosing may resume only after their AE has resolved and only if it would be considered safe to do so in the assessment of the Investigator (and in consultation with the Medical Monitor). For patients who have discontinued dosing, the patient will continue to be followed for 12 weeks after their final dose or until the resolution of any ongoing clinically significant AE, whichever occurs later. (For the definition of AE resolution, please refer to [Section 10.2.1.](#))

Dosing of SRK-015 for an individual patient may also be suspended or discontinued for safety concerns other than those described above based on review by the SST or at the discretion of the Investigator if he/she feels the patient's safety may be threatened. The Investigator may ask for an ad hoc SST meeting to be held for any single event or combination of events that in his/her professional opinion may jeopardize the safety of the patient or the reliability of the data.

Patients who develop either an SAE or other toxicity meeting the individual stopping criteria will be carefully monitored, which may include the following at the discretion of the Investigator:

- Additional clinical laboratory tests and/or other clinical investigations
- Additional visits or extended duration of follow-up
- Obtaining a specialist consultation

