10.3. Adverse Event Monitoring

Each patient will be monitored for the occurrence of AEs, including SAEs, from the signing of the ICF through the final follow-up visit.

- Patients will be questioned and/or examined by the Investigator or a qualified designee for evidence of AEs. The questioning of patients with regard to the possible occurrence of AEs will be generalized such as, “How have you been feeling since your last visit?” The presence or absence of specific AEs should not be elicited from patients.
- Patients having AEs will be monitored until resolution or stabilization (in the case of persistent impairment), or until the event becomes chronic in nature, or the patient dies.
- AEs, actions taken as a result of AEs, and follow-up results must be recorded in the eCRF as well as in the patient's source documentation. Follow-up laboratory results should be filed with the patient's source documentation.

For any SAEs or AEs that require the patient to be discontinued from dosing, relevant clinical assessments and laboratory tests will be repeated as clinically appropriate, until final resolution or stabilization of the event(s). Patients will continue to be followed through 12 weeks after the final dose.

All safety laboratory analyses will be performed at a central laboratory. The clinical laboratory values will be reported to the Investigator who will review them for clinical significance and consideration of abnormal values as potential AEs.

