2.3.2.1 Adverse Events

An AE is any untoward medical occurrence in a patient or clinical trial patient administered a pharmaceutical product that does not necessarily have to have a causal relationship with the treatment administered. An AE can therefore be any unfavorable or unintended sign (including an abnormal laboratory finding), symptom, or disease temporally associated with the use of a medicinal product, whether or not it is related to the medicinal product.

- AEs may be new events or may be pre-existing conditions that have become aggravated or have worsened in severity, seriousness or frequency from Baseline at any time during the study.
- AEs may be clinically significant changes from Baseline in physical examination, laboratory tests, or other diagnostic investigation (e.g., laboratory results, x-ray findings).

Adverse events will be coded using the Medical Dictionary for Regulatory Activities (MedDRA) Version 23.0 or later.

The severity of AEs will be graded using the National Cancer Institute (NCI) Common Terminology Criteria for Adverse Events (CTCAE), Version 5.0. The causal relationship between the study drug and the AE will be assessed using one of the following categories:

- Not Related: Factors consistent with an assessment of Not Related include:
 - Temporal relationship is lacking (e.g., the event did not occur within a reasonable time frame following administration of the study drug); or
 - Other causative factors more likely explain the event (e.g., a pre-existing condition, other concomitant medications).
- Related: Factors consistent with an assessment of Related include:
 - There is a positive temporal relationship (e.g., the event occurred within a reasonable time frame following administration of study drug); or
 - The AE is more likely explained by the investigational product than by another cause (e.g., the AE shows a pattern consistent with previous knowledge of the investigational product or the class of the investigational product).

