3.1.2 Analysis Visits

Scheduled post-baseline assessments will be assigned to an analysis visit based on the visit captured in EDC. Unscheduled post-baseline and early termination assessments for motor function outcome measures will be assigned to an analysis visit based on the calculated Analysis Day and windows defined in the following table:

Visit	Analysis Visit	Analysis Day Target	Analysis Day Window
Visit 4/Day 56	Visit 4/Week 8	57	44 - 99
Visit 6/Day 112	Visit 6/Week 16	113	100 – 155
Visit 8/Day 168	Visit 8/Week 24	169	156 - 211
Visit 10/Day 224	Visit 10/Week 32	225	212 - 267
Visit 12/Day 280	Visit 12/Week 40	281	268 – 351
Visit 15/Day 364	Visit 15/Week 52	365	352 - 379
Visit 16/Day 392	Visit 16/Week 56	393	380 - 421
Visit 17/Day 448	Visit 17/Week 64	449	>421
Visit E1/Day 364	Visit E1/Week 52	365	352-379
...		...	(target date-13 days to the next target date - 14 days)

For each analysis visit, if a scheduled visit is captured in EDC, then the measurement from this scheduled visit will be used as the measurement for the analysis visit. If no scheduled visit is captured in EDC, the unscheduled measurement within the window closest to the target date will be used. Visits that occurred outside a +/- 28-day window of the target date used as analysis visits will be listed. For safety measurements, unscheduled and ET visits will not be re-assigned and will be listed, and the ET visit will be summarized separately.

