3.6.2 Laboratory Assessments

Descriptive statistics for each parameter will be presented for baseline, each visit, and the change from Baseline. The 95% CI based on the Student's t-distribution for the change from Baseline will be presented.

Frequency tables will be provided to display the number and percentage of patients with laboratory abnormalities after administration of study drug.

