3.6.4 Electrocardiograms (ECGs)

Summary statistics for continuous ECG parameters and the change from Baseline, along with the 95% CI based on the Student's t-distribution, will be presented by treatment group for each scheduled visit. Counts and percentages of the overall interpretation of the ECG findings will be

presented by treatment group for each scheduled visit. The 12-Lead Electrocardiogram data will be listed by patient.

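### Abnormal ECGs from unscheduled visits reach no ECG table, no per-patient post-dose ECG count is planned, and the laboratory abnormality count does not say whether unscheduled and ET values are included

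*Combined protocol and SAP*

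**What the plan says.** **Visit assignment.** SAP 3.1.2 treats motor function and safety data differently. For motor function, "Unscheduled post-baseline and early termination assessments for motor function outcome measures will be assigned to an analysis visit". For safety, "For safety measurements, unscheduled and ET visits will not be re-assigned and will be listed, and the ET visit will be summarized separately".

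**ECG.** Under SAP 3.6.4, the overall ECG interpretation is "presented by treatment group for each scheduled visit. The 12-Lead Electrocardiogram data will be listed by patient". On why off-schedule tracings exist, Protocol Table 2, footnote j (Section 6.2) says: "Unscheduled ECGs may be performed as clinically necessary".

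**Laboratory.** SAP 3.6.2 says: "Frequency tables will be provided to display the number and percentage of patients with laboratory abnormalities after administration of study drug". Protocol 6.3.4 allows, for patients with a serious event or other toxicity meeting the individual stopping criteria, "Additional clinical laboratory tests and/or other clinical investigations".

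**AE route.** Protocol 10.3 says: "The clinical laboratory values will be reported to the Investigator who will review them for clinical significance and consideration of abnormal values as potential AEs". SAP 2.3.2.1 adds: "AEs may be clinically significant changes from Baseline in physical examination, laboratory tests, or other diagnostic investigation".

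**Purpose.** Safety and tolerability is a primary objective (SAP 2.1.1), and SAP 3.1.5 says that the aim for safety is estimation of event rates.

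**The concern.** A tracing taken for clinical need is more likely to be abnormal than a routine one. If such tracings are left out of the counts, the omission depends on the outcome, and any incidence read from the tables tends to be too low.

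A by-visit table also shows how many patients are abnormal at each visit, not how many are ever abnormal. A patient abnormal at two visits is counted twice, and one abnormal only between visits is not counted. Without a per-patient count, neither can be corrected from the tables.

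Scheduled timing makes this matter more. In the Treatment Period and Extension Periods A and B, ECGs on dosing days are taken within the 2 hours before infusion. Only Extension Period C adds post-infusion tracings, at EC1 and EC13 (Protocol 10.1.5). Outside those two visits, an ECG change during or soon after an infusion could be seen only on an unscheduled tracing.

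**Working it through.** The plan states no figure on this point, so there is none to reproduce. The check is a reading of the rules, followed by an illustration of size on stated assumptions.

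**Step 1. Where each measurement goes**

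| Source of value | ECG | Laboratory |
|---|---|---|
| Scheduled visit | By-visit interpretation count (3.6.4) | By-visit statistics and per-patient abnormality count (3.6.2) |
| Unscheduled visit | Listing only (3.1.2 with 3.6.4) | Listed (3.1.2); not stated whether also in the per-patient count |
| ET visit | Separate ET summary (3.1.2) | Separate ET summary (3.1.2); not stated whether also in the per-patient count |
| Patient-level count over all post-dose values | None described | Described, but which visits feed it is not stated |

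For ECG, the unscheduled row follows directly from the two sections. For laboratory data, the 3.6.2 table is already per patient, post-dose and not tied to a visit. Sections 3.1.2 and 3.6.2 can be read together in two ways, and two programmers could produce different counts.

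**Step 2. What the AE tables recover**

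The AE tables (SAP 3.6.1) are not limited to scheduled visits. Under SAP 2.3.2.1, a diagnostic finding can be an AE when the change is clinically significant. Protocol 10.6.1.2 keeps abnormal laboratory values and vital signs out of AE reporting unless they need action, come with signs or symptoms, or are judged significant. It does not name ECG. The AE tables therefore recover findings above a clinical threshold, whereas an abnormality table has a lower one. The certain loss is the abnormal unscheduled ECG not recorded as an AE.

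**Step 3. Weight of one patient**

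Cohort sizes are in SAP 2.2.1. One omitted patient changes a rate by 1/20 = 5.0 points in Cohort 1, 1/15 = 6.7 points in Cohort 2, and 1/10 = 10 points in one dose arm of Cohort 3 (20 patients split 1:1).

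**Step 4. Illustration over a range**

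Inputs: N = 55 planned patients (SAP 2.2.1). Assumed, not in the documents: a true incidence p of 5% or 10%, and a share s, from 0 to 50%, of affected patients whose abnormality shows only at an unscheduled visit. All other affected patients are taken to be caught on schedule.

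- Tabulated incidence = p × (1 − s)
- Expected patients tabulated = 55 × p × (1 − s)
- Chance of tabulating at least one = 1 − [1 − p(1 − s)]^55

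| s | p = 5%: expected patients | p = 5%: chance of at least one | p = 10%: expected patients | p = 10%: chance of at least one |
|---|---|---|---|---|
| 0% | 2.75 | 94.0% | 5.50 | 99.7% |
| 10% | 2.48 | 92.1% | 4.95 | 99.4% |
| 25% | 2.06 | 87.8% | 4.13 | 98.6% |
| 50% | 1.38 | 75.2% | 2.75 | 94.0% |

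A count that uses any post-dose reading, including unscheduled and ET, gives the s = 0 row whatever s is. The table applies to ECG as the SAP stands, and to laboratory data only if 3.6.2 is programmed from scheduled visits alone.

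**The case against.** Several counter-arguments carry weight.

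- **Keeping clinically triggered values out of by-visit means is sound.** This stands, and the fix keeps it.
- **Important findings become AEs.** This stands for findings judged clinically significant. It does not cover those below that threshold. The SAP 3.6 remark that clinically significant outcomes will be noted specifies no table.
- **Not every unscheduled ECG is prompted by a suspicion.** The schedules also mark ECG in the unscheduled-visit column, so some tracings may simply accompany a visit made for another reason. This stands: omitting those loses information but need not bias the count. It is one reason the size cannot be stated.
- **All data are listed, and about 55 patients can be reviewed by hand.** True (SAP 7), but a listing gives no rate.
- **The table mock-ups are in separate documents (SAP 7).** True; the absence of a patient-level ECG count is established for the SAP text only.

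Three stronger readings are tempting, and the documents do not support them.

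- A reader might infer that unscheduled laboratory values are excluded from the abnormality count. SAP 3.1.2 concerns assignment to visits, and the 3.6.2 table does not depend on visits. The text is unclear and states no exclusion.
- A reader might infer that ET values are lost. They are tabulated, as a separate visit.
- A reader might divide an assumed duration of abnormality by the spacing of scheduled ECGs to get a percentage missed. The documents give no durations. The spacing also varies: as the tables extract, 4, 12, 16 and 16 weeks between Treatment Period ECGs from Day 0 to Day 336, and 12 weeks in Extension Period A, then 8 from E11 to E13. The calculation would also need every abnormality missed on schedule to be found at an unscheduled visit. Silent ones might never be found.

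**Conclusion.** The point holds for ECG as a gap in the SAP text: an abnormal unscheduled tracing enters no ECG table unless it is also an AE, and no per-patient post-dose ECG count is described. This can understate the incidence of ECG abnormality. The amount cannot be estimated from the documents; on the assumed range above, the understatement equals the share s, from nothing to half.

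For laboratory data, the finding is an ambiguity about which values feed an otherwise suitable table. For ET data, the finding is only that the values stand apart and are not combined with other visits in any patient-level ECG count.

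A general statement that the plan understates safety incidence would go too far, because AE tables are open to findings from any visit. This is an inexpensive improvement to the reporting of a primary objective, not a flaw that undermines the safety analysis.

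**What to change.** 1. **SAP 3.1.2:** limit the rule that unscheduled values are only listed, and ET values summarised apart, to by-visit summaries. Keep those summaries on scheduled visits.
2. **SAP 3.6.4:** add a per-patient count of any ECG abnormality after the first dose, taking each patient's worst interpretation over scheduled, unscheduled and ET readings, by cohort and dose, with the Safety Population as denominator.
3. **SAP 3.6.2:** state that the laboratory abnormality count uses any post-dose value, including unscheduled and ET.

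No new data are needed. The cost is SAP wording and one extra ECG table. Reported abnormality rates may rise, and a footnote should say that clinically triggered readings are included.

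Protocol 6.2 records a 12-month database lock, so if the change comes after it, label the 12-month table as added. The change can still be prospective for the Extension Periods, where the 12-month methods carry over (SAP 3.1) and content is approved before each analysis (SAP 5.3).

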3.1.3 Definition of Baseline

Baseline for all efficacy and safety variables will be defined as the last measurement prior to the first dose of study drug.

3.1.4 Summary Statistics

[figure not shown]
Descriptive statistics (number of patients, mean, standard deviation, median, minimum, and maximum) will be used to summarize the continuous data. Discrete measures will be summarized using counts and percentages.

3.1.5 Hypothesis Testing

No formal statistical testing will be applied for the interim or 12-month analyses.

Regarding safety, the purpose is to estimate the event rates. The figure below can serve as a guideline to inform safety. For example, for a given event type if an event rate of 1/35 or more would be of safety concern, and the true rate of this type of event is 5%, then there is about a 50% probability to report such concern in the study.

Figure 5: Probability of the True Incidence Rate as Shown Will Be Identified Under Different Scenarios as the Number of Patients in the Study Accrue

3.1.6 Evaluation of Site Effect

This is a multicenter study enrolling patients from approximately 20 study sites across the United States and Europe. Site effect will not be evaluated for any planned analysis since the number of patients at each site is expected to be too small for such evaluation.

3.1.7 Handling of Dropouts and Missing Data

3.1.7.1 Missing or Incomplete Dates

Dates will be printed in ISO 8601 date format (YYYY-MM-DD). If only year and month are available, date will be displayed as YYYY-MM. If only year, then just YYYY. Dates that are

missing because they are not applicable for the patients will be output as “NA”, unless otherwise specified.

Adverse events with missing start dates will be considered as treatment-emergent unless the partial date excludes that possibility, e.g., the adverse event month is prior to the study drug administration month. Otherwise, the first day of the month will be used to impute missing start days and January will be used to impute missing start months. If the causality for an adverse event is missing, the adverse event will be assumed to be related.

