11.2.1. Safety Analyses

Safety data will be evaluated for vital signs, laboratory outcomes, concomitant medications, ECGs, and AEs. Clinically significant outcomes will be noted. Vital signs and laboratory outcomes will be summarized within each treatment group within all cohorts and the 2 dose groups within Cohort 3. AEs will be coded in the Medical Dictionary for Regulatory Activities; the emphasis will be on treatment-emergent adverse events (TEAEs); the TEAE type, incidence, severity, relationship, onset and resolution time will be displayed descriptively. The incidence rate of AEs and TEAEs will be reported.

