2.3.2.2 Treatment-Emergent Adverse Events

Treatment-emergent adverse events (TEAEs) are defined as those AEs satisfying one of the following:

- Occur after the first administration of study drug; or
- Occur prior to the administration of study drug and worsen in severity/grade or relationship to investigational medication after the administration of study drug.

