3.1.1 Analysis Day

Analysis day will be calculated using the first dose date of study drug as the reference. Analysis day = date - date of first dose +1 according to Clinical Data Interchange Standards Consortium (CDISC) standards. The day the patient takes the first dose is Analysis Day 1. The day before Analysis Day 1 is Analysis Day -1.

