3.6.1 Adverse Events (AEs)

A summary overview of TEAEs will be provided, which presents the number and percentage of patients in each cohort and dose level from the Safety Population satisfying each of the following categories:

- Any AEs,
- Any SAEs,
- Any TEAEs,
- Any AEs leading to death,
- Any AEs leading to study drug discontinuation,
- Any SAEs leading to death,
- Any SAEs leading to study drug discontinuation,
- Any TEAEs leading to death, and
- Any TEAEs leading to study drug discontinuation,

Adverse events will be coded using the Medical Dictionary for Regulatory Activities (MedDRA) version 23.0 or later. The number and percentage of patients with specific criteria will be summarized by their MedDRA preferred term within system organ class and by treatment within each cohort. These summaries will include patients with the following criteria: TEAEs, SAEs, TEAEs with severity of Grade 3 and above, drug related TEAEs, TEAEs present in 5% or more of patients, and various categories of TEAEs by Time (on or before Week 12 vs. Post Week 12). For patient count summaries, multiple AE events with the same MedDRA coded terms (preferred term and system organ class) from the same patient will only be counted once.

The number and percentage of patients with TEAEs will be summarized by reported maximum severity within each MedDRA preferred term within system organ class and by dose-level within each cohort.

All SAEs will be listed with an indication of whether the SAE was treatment emergent or started prior to treatment. All TEAEs that are reported as leading to study drug discontinuation will be listed. TEAEs leading to death, if applicable, will be listed.

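### Partial AE start dates are imputed with no floor at the first dose: flagged TEAEs can get a pre-dose onset, and day-missing events in the Week 12 month all count as early

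*Combined protocol and SAP*

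**What the plan says.** SAP 3.1.7.1 has two rules for incomplete AE start dates. The first sets the flag: "Adverse events with missing start dates will be considered as treatment-emergent unless the partial date excludes that possibility". Its example of an excluded event is one where "the adverse event month is prior to the study drug administration month", so an event in the same month as the first dose stays treatment-emergent. The second, introduced by 'Otherwise', sets the date: "the first day of the month will be used to impute missing start days and January will be used to impute missing start months". Neither rule mentions the first dose date as a lower limit, and no other section supplies one.

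Three places use the result:
- SAP 2.3.2.2 defines a TEAE as an event satisfying "Occur after the first administration of study drug", or as a pre-dose event that worsens after dosing.
- SAP 3.6.1 tabulates TEAEs by time, split at Week 12, with no rule for partial dates at the cut.
- Protocol 11.2.1 says that "the TEAE type, incidence, severity, relationship, onset and resolution time will be displayed descriptively".

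Onset is counted from the first dose (SAP 3.1.1: "Analysis day = date - date of first dose +1"). AEs are collected "from the signing of the ICF through the final follow-up visit" (protocol 10.3), so genuine pre-dose events sit in the same dataset.

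**The concern.** The flag rule gives the benefit of the doubt to treatment emergence, while the date rule always takes the earliest possible day. Applied to the same record, they can disagree: the event is counted as a TEAE, but its imputed onset lies before any drug was given. Such a record gives a negative onset day in any display of TEAE onset time.

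The earliest-day rule also errs in one direction only. The imputed date can equal the true date or precede it, but never follow it. This matters at the Week 12 split, where a day-missing event in the month that contains the cut is always counted as early. With about 55 patients in three cohorts, a few such events could visibly change a row of the by-time table.

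**Working it through.** The plan gives no figure for this rule, so there is none to reproduce. I applied the rule to calendar dates.

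**Inputs.** The two rules and the day numbering come from SAP 3.1.7.1 and 3.1.1. First-dose dates and event dates are not given. *Assumptions:* first-dose dates spread evenly over 1 January to 31 December 2019, or over 1 May 2019 to 21 January 2020; event dates spread evenly; Week 12 cut at first dose plus 83 or plus 84 days. The last dosing date is bounded by the 12-month database lock in protocol 6.2: 19 January 2021 minus 364 days is 21 January 2020.

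**1. One record.** Take a first dose on 20 June 2019 and an AE recorded as 2019-06. The AE month is not before the dosing month, so the event is a TEAE. Its start is imputed to 1 June, which is 20 − 1 = 19 days before dosing. By that date it did not start after the first dose, and nothing shows that it is a worsened pre-dose event.

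**2. How often, in the first-dose month.**
- By dosing day, 30-day month: the imputed date precedes dosing on 29 of 30 days (96.7%), and the mean gap is (0 + 1 + … + 29)/30 = 14.5 days. On the 2019 calendar it is 353 of 365 dosing dates, also 96.7%.
- By event: if dosing is on day d, the possible on-treatment days number 31 − d. These sum to 465 over d = 1 to 30, and only the 30 belonging to d = 1 escape. So 435/465 = 93.5% are dated before dosing. Calendar enumeration gives 93.6% for both dosing ranges.

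**3. Week 12, day missing.** The first of the month that contains the cut is never after the cut, so 100% of these events are placed early. The share truly later is the mean of (30 − d)/30 over d = 1 to 30, or 14.5/30 = 48.3%. Enumeration gives 48.4% to 48.6% across both ranges and both cut definitions. In the example, 20 June plus 84 days is 12 September. An AE recorded as 2019-09 goes to 1 September and counts as early, although 18 of the 30 days in that month (13th to 30th) fall after the cut.

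Every other month lies wholly on one side of the cut and is classified correctly. That includes the first-dose month, whose events belong in the early period whether dated to the 1st or to the first dose. Of day-missing events within 14 days either side of the cut, about 88% are placed early; the other 12% fall in the next calendar month and are correctly placed late.

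**4. Year only.** For true onsets from the first dose to Day 364, 38% to 50% are imputed before the first dose. Between 66% and 70% are placed on or before Week 12 (pre-dose included), against 23% truly early. The rest go late, because 1 January of the following year can fall after Week 12.

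**5. Effect of a floor.** With the later of the first of the month and the first dose date, the 94% in step 2 falls to 0%. The floor does not change the cut-month result in step 3, which needs its own rule.

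**The case against.** The strongest reply is that the exposure is small and the consequence mild. Sites contact patients within 7 days of each Treatment Period infusion (protocol 6.1), visits are every 4 weeks, and protocol 14 requires full source verification with queries, so partial dates should be few. Partial dates are printed as collected, all SAEs are listed with their treatment-emergent status, there is no formal testing (SAP 3.1.5), and programming specifications are in separate documents (SAP 7). All this limits the effect. It does not settle which onset date a TEAE should carry in a derived table.

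A second reply is that a pre-dose imputed date may be true. AEs are recorded from consent and screening runs up to 28 days before dosing, so some first-month events did begin before the drug. That is fair, but the SAP has already chosen to call such events treatment-emergent, and the date it assigns then contradicts that choice.

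A third reply turns on 'Otherwise', which can be read as confining imputation to events already excluded as treatment-emergent. The conflict then disappears, but TEAEs have no imputed date and the SAP does not say how to place them at Week 12. A reader might infer that the table is wrong on either reading. That does not follow: comparing months would still place every day-missing event outside the cut month. This reading leaves some cases undefined; it does not by itself produce a wrong table.

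**Conclusion.** The point holds as a minor defect in a stated rule. On the natural reading, SAP 3.1.7.1 gives a pre-dose onset to TEAEs whose partial date matches the first-dose month, or the first-dose year if the month is also missing, unless dosing fell on the imputed day. It also counts all day-missing TEAEs in the cut month as early, although about half would be later. The percentages rest on evenly spread dosing and event dates and concern partial-date events only. The documents give no count of these, so no absolute effect can be computed.

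Three stronger conclusions are tempting but not supported. A reader might infer that true TEAEs are lost; they are not, because the flag is set from the partial date before any imputation, and they would be lost only if a programmer re-derived the flag from the imputed date. A reader might infer that all events near Week 12 move early; complete dates are untouched, day-missing events in the following month are placed late correctly, and year-only events can go late. Finally, a reader might suppose that the Week 12 split exists to reveal late-onset harm; SAP 3.6.1 gives no purpose for it.

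**What to change.** Replace the 'Otherwise' sentence in SAP 3.1.7.1 with:

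> Treatment emergence is determined from the partial date, and from the AE end date if it precedes the first dose. For AEs so classified as treatment-emergent, a partial start date is imputed as the later of the first dose date and the first day of the known month (or 1 January of the known year), and a wholly missing start date as the first dose date, but not after the AE end date. For other AEs, the first day of the month or January is used.

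The end-date clause in the first sentence matters: without it, the cap at the end date could bring back a pre-dose onset for a flagged event.

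Add to SAP 3.6.1 that partial-date TEAEs which cannot be placed relative to Week 12 are counted in a separate row of the by-time table.

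The cost is a few SAP sentences and minor programming, with no new data. The downside is that a few AEs may appear in the extra row.
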